OSA is a multifactorial disease with different manifestations – Endotypes and Phenotypes: OSA is increasingly recognized as a multifactorial disorder i.e., different people have OSA for different reasons. Although an anatomical predisposition (collapsibility of the upper airway) is generally required, other factors are important as well, including a low respiratory arousal threshold (wake up too easily), dysfunction in upper airway dilator muscles and instability in ventilatory control (which we quantify using the engineering term loop gain [LG]) which leads to periods of decreased pharyngeal tone.⁴⁰ The ultimate goal of our work is to personalize therapy for OSA one day by addressing the underlying endotype to treat OSA effectively in an individual with targeted therapy.⁴¹

Different patients with OSA may also have different symptoms, and variable risk of certain co-morbidities. That is, two patients of the same gender, weight and OSA severity, as defined by the apnea-hypopnea index (AHI), may have very different observable consequences of OSA, or phenotypes. The concept of OSA phenotypes has been advanced by multiple groups. For example, Ye and colleagues found 3 distinct clusters of OSA types based on sleep questionnaire responses, which they labelled the “disturbed sleep”, “minimally symptomatic”, and “excessive daytime sleepiness” groups.⁴² The clusters did not differ based on sex, BMI, or sleep apnea severity. However, the clusters did vary in associations with hypertension and cardiovascular disease, a finding consistent with other studies.^{43,44} Although AHI is frequently used to assess OSA severity, AHI does not correlate strongly with most relevant OSA co-morbidities.^{45,46} A related observation is that while treatment of CPAP can improve blood pressure, the effect is highly variable across individuals.⁴⁷ Taken together, these observations suggest that the expression of OSA in an individual is often variable.

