If subjects are not found to have OSA, they will not continue with the study.

(End of Aim #1)

Aims #2 and #3

Subjects found to have OSA (with AHI >5 events/hour) will be referred for clinical evaluation (by a sleep physician not involved in the study) and treatment, and will also return for overnight visit #2, and continue to be followed with weekly phone calls and a repeat assessment 3 months after starting OSA treatment.

Overnight Visit #2 (Aim #2) Measurement of Endotypic Traits

This visit will be scheduled to occur within 1 month of visit 1, and will be prior to any clinical OSA treatment. Subjects will come to the sleep research laboratory about 2-3 hours before their usual bedtime. They will undergo polysomnography, as described above, without the physiological CPAP testing procedure. To review, the subject will have EEG, EMG, EOG, and ECG electrodes, an adhesive body position sensor placed in standard locations. Pulse oximetry sensor will be attached either to a finger or ear lobe and secured by tape. The following parameters will be measured during sleep: electroencephalogram, eye movement, electrocardiogram, electromyogram, leg movement, snoring sounds, nasal pressure, and nasal-oral air flow by thermistor, respiratory effort and body position by piezo-electric bands of the thorax and abdomen or magnetometers, position sensors, and pulse oximetry. This equipment is standard for diagnostic polysomnography and should not be uncomfortable.

Additional equipment for the physiological sleep study will also be applied to the subject, as follows:

A thin esophageal catheter (6-8 french) with an electrode array to measure diaphragm electromyography will be placed via the nares. Prior to the cannula placement the subject will receive 2 sprays of a nasal decongestant (0.05% oxymetazoline hydrochloride), followed by 4% lidocaine topical spray for local anesthesia. The catheter will be confirmed to be in the proper position by examining the signal, then taped to the nose (and later secured to the CPAP mask). The esophageal catheter placement may be omitted by subject or investigator request; in this case subjects can still remain in the study.

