Obstructive Sleep Apnea Endotypes and Impact on Phenotypes of People Living With
HIV

Statistical Analysis Plan

NCT03575143

October 5, 2018

Statistical Considerations:

Results will be reported as point estimates (odds ratios or mean differences across groups, as appropriate) and interval estimates (95% confidence intervals). All tests of significance for the secondary outcomes will be 2-sided and Bonferroni adjustments will be made for multiple comparisons as appropriate. A p-value of 0.05 will be considered statistically significant. Statistical analysis will be conducted using the statistical software R 3.3.3. (www.rproject.org). Demographic and baseline characteristics will be compared among the cases and controls using Fisher's exact test for categorical variables, and a two-sample t-test for continuous variables. Appropriate non-parametric alternatives will be considered, if parametric assumptions fail.

Aim 1 – Sleep and Activity Phenotyping

To compare the symptoms of PLWH+OSA vs. PLWH–OSA. This aim will allow us to test the hypothesis that fatigue is overexpressed in PLWH+OSA compared to PLWH–OSA, independent of known covariates.

Sample Size Justification: The study is expected to enroll 120 evaluable HIV subjects, not known to have OSA, or not on treatment for OSA, and not known to have any other sleep disorder (such as narcolepsy) other than symptoms of insomnia. Based on the literature cited above, we expect to find a 50% prevalence of OSA (defined as an AHI >5/hour using 4% criteria) such that 60 subjects will have OSA and 60 will not. FACIT-F scores in HIV have been reported by two groups with remarkably similar means and standard deviations (Ref 64, 108). The presence of witnessed apneas was associated with a 6.5 reduction in FACIT score (with 3 points considered clinically meaningful, lower scores are associated with worse fatigue). Therefore, assuming a mean FACIT-F score of 36 in those without OSA and 30 in those with OSA, and a standard deviation of 12 in both groups, we will have approximately 80% statistical power to detect a difference between the two groups. Power is based on a two-sided, two-sample t-test, assuming alpha is set to 0.05. To account for 10% attrition, we will enroll 134 subjects to achieve 120 evaluable subjects.

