Statistical Analysis Plan: First, we will evaluate if there is a difference in the primary outcome, FACIT-F scores, between OSA and non-OSA participants using a two-sample t-test. Multiple regression modeling will be used to assess the association between FACIT-F scores and OSA status (dichotomous independent variable), adjusting for other potential covariates, such as age, OSA severity (AHI), medications, mean sleep duration as assessed by actigraphy, and inflammation as assessed by CRP or similar such as IL-6.

Aim 2 – OSA Endotyping

Data Analysis: From the research PSG, the upper airway collapsibility as defined by the critical closing pressure (Pcrit) will be analyzed according to published methods. Additionally, the relevant traits will be extracted with the aid of MATLAB (Natick, MA) and our custom software. The traits will then be plotted on the axes ventilation vs. ventilatory demand to produce an individual assessment of the relevant traits for each subject

Aim 2: In those PLWH found to have OSA, we will perform detailed physiological assessments to determine endotype. This aim will allow us to test the following hypotheses:

Hypothesis 2A: To compare neurocognitive performance (PVT) in PLWH+OSA with a low arousal threshold (wake up too easily) vs. those with a high arousal threshold. This aim will allow us to test mechanistically the hypothesis that stratified for similar disease

severity, low arousal threshold induced OSA yields worse neurocognitive dysfunction compared to equal severity OSA with high arousal threshold.

Hypothesis 2B: To compare endothelial dysfunction via arterial tonometry in PLWH and OSA with a high loop gain (ventilatory instability with associated hypoxemia/hypercapnia) vs. those with low LG. This aim will allow us to test the hypothesis that stratified for similar disease severity, LG-induced OSA yields worse endothelial function compared to equal severity OSA with low LG.

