Sample Size Justification: Of the 120 PLWH studied in Aim 1, we believe that at least 60 will have OSA. We will split the cohort of those with OSA into high and low arousal threshold at the median value for the group. Although we will have multiple markers of cognitive function, our main outcome for Aim 2A for statistical purposes will be the psychomotor vigilance test (PVT). Prior work by Kribbs and colleagues reported a mean reciprocal reaction time of 3.9 seconds⁻¹ with a standard deviation of 0.5 (Ref 112). We believe that a change of 0.3 seconds⁻¹ represents a clinically important difference based on the effect size of CPAP observed with prior studies (Ref 123). Therefore, assuming a mean reciprocal reaction time of 3.9 seconds⁻¹ in those with low arousal threshold OSA and 4.2 seconds⁻¹ in those with high arousal threshold OSA, and a SD of 0.5 in both groups, we will have adequate power (beta >0.8) to detect a difference between the two groups (alpha = 0.05).

Statistical Analysis Plan: We will evaluate if there is a difference in PVT in OSA participants with low vs high AT using a two-sample t-test. As a sensitivity analysis, we will consider multiple regression models adjusting for additional covariates such as age, AHI, medications, mean sleep duration via actigraphy, and inflammation as assessed by CRP or IL-6 may be included in the modeling if significantly associated with outcome (p<0.10).

Aim 3 – Impact of OSA treatment on Sleep and Activity Phenotypes

To test in PLWH+OSA whether 3 months of PAP treatment results in changes in OSA manifestations. This aim will allow us to test the hypothesis that endotype underlying OSA will be predictive of the specific clinical improvements seen in adherent users of PAP therapy. For example, those with high LG at baseline will have the greatest improvement in endothelial dysfunction with PAP therapy compared to other OSA patients with similar disease severity as measured by AHI.

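### The Aim 1 regression lists AHI as a possible covariate beside OSA status, which is AHI cut at 5; with both entered, the OSA coefficient is not the adjusted OSA versus non-OSA difference

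*SAP*

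**What the plan says.** The SAP's Aim 1 sample size paragraph gives the definition of OSA: "defined as an AHI >5/hour using 4% criteria". The protocol uses the same cut-off in section 9, under Aims #2 and #3: "Subjects found to have OSA (with AHI >5 events/hour) will be referred for clinical evaluation".

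The hypothesis for Aim 1 is that "fatigue is overexpressed in PLWH+OSA compared to PLWH–OSA, independent of known covariates". Two analyses are planned in the SAP's Aim 1 Statistical Analysis Plan. The first is unadjusted: "First, we will evaluate if there is a difference in the primary outcome, FACIT-F scores, between OSA and non-OSA participants using a two-sample t-test". The second is a multiple regression with OSA status as a dichotomous independent variable, "adjusting for other potential covariates, such as age, OSA severity (AHI), medications", followed by actigraphic sleep duration and an inflammation marker.

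Neither document makes OSA status and AHI alternatives, confines AHI to the OSA group, or says how the OSA coefficient should be read once AHI is included. Aim 1 also has no covariate selection rule. The p<0.10 screen appears only under Aims 2 and 3.

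**The concern.** OSA status is a deterministic function of AHI: two participants with the same AHI cannot differ in OSA status. Holding AHI fixed while OSA status changes therefore compares people who do not exist, and the model fills the gap by extrapolating its AHI term to the cut-point.

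The regression carries weight because the t-test is unadjusted and cannot speak to the covariate-independent part of the hypothesis. The SAP's Statistical Considerations promise point estimates with 95% confidence intervals, so readers would take this coefficient as the adjusted OSA effect. If fatigue worsens steadily with AHI, the coefficient could be small and non-significant, and could be reported as showing that OSA is not independently associated with fatigue when its severity is what drives the fatigue.

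**Working it through.** **1. The plan's own figure.** Inputs from the SAP's Aim 1 sample size paragraph: 60 per group, means 36 and 30 (difference 6), SD 12, two-sided alpha 0.05.

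- Standard error = 12 × √(2/60) = 2.19.
- Normal approximation: power = Φ(6/2.19 − 1.96) = 0.782. The exact t-test gives 0.775.

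Both agree with the stated figure of approximately 80%. This power belongs to the model without AHI.

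**2. What the coefficient means.** Write the regression, other covariates omitted, as

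E(FACIT-F) = β0 + β1·OSA + β2·AHI, with OSA = 1 if AHI > 5.

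- Group difference = β1 + β2 × (mean AHI with OSA − mean AHI without OSA).
- β1 alone is the vertical gap between two parallel lines, that is, the modelled step at AHI 5.

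The two are equal only if β2 = 0. This needs no assumption about the data. If the true relation is not linear in AHI, β1 is a model-dependent offset, which is still not the group difference.

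**3. A worked case.** Assume AHI is log-normal with median 5 (to give the SAP's 50% prevalence) and log-SD 1.0.

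- Difference in mean AHI between the groups = 2 × 5 × exp(0.5) × (2Φ(1) − 1) = 16.49 × 0.683 = 11.26.
- If fatigue is linear in AHI and the group means differ by −6, then β2 = −6/11.26 = −0.53 points per event/hour, and β1 = −6 − (−0.53 × 11.26) = 0.

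The whole 6-point difference sits in the slope.

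**4. Simulation.** Assumptions: n = 120, log-normal AHI with median 5 and log-SD 0.8 / 1.0 / 1.2, true group difference −6, total within-group SD 12 as in the SAP, raw AHI as the covariate, 5,000 runs per scenario. Unadjusted power was 0.77 to 0.81. With AHI added:

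| True shape | OSA coefficient | Power | 95% CI covers −6 |
|---|---|---|---|
| Step at AHI 5 | −6.05 / −6.11 / −6.02 | 0.55 / 0.61 / 0.65 | 95% |
| Linear in log AHI | −2.99 / −3.75 / −4.20 | 0.19 / 0.29 / 0.39 | 82% / 87% / 89% |
| Linear in AHI | −0.02 / −0.01 / −0.05 | 0.04 / 0.05 / 0.04 | 40% / 32% / 22% |

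A mixed shape, half step and half linear in AHI, was run with SD 12 taken as the residual SD about the curve. It gave −3.04 / −2.98 / −3.06 with power 0.19 / 0.20 / 0.22. Under that convention unadjusted power was 0.70 to 0.78.

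**5. Check on the step row.** The average OSA-AHI correlation in samples of 120 was 0.64 / 0.57 / 0.51, and the average variance inflation was 1.74 / 1.53 / 1.38. At 1.53 the standard error is 2.19 × √1.53 = 2.71, and power = Φ(6/2.71 − 1.96) = 0.60, in line with the simulated 0.61.

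**6. Sensitivity to the assumed spread and scale.** In very large samples, with log-SD from 0.6 to 1.5, the inflation runs from 1.88 down to 1.09, and power under a pure step from 0.51 up to 0.75. If a logged AHI is entered instead, the inflation is about 2.8 and power about 0.37.

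**The case against.** The strongest reply is that the list is only illustrative. AHI is called a potential covariate, nothing commits the analyst to entering it, the regression is secondary to the t-test, and the SAP claims no power for it. This stands as a limit on scope. But AHI is named expressly and Aim 1 has no rule that would keep it out. If the p<0.10 screen from the later aims were borrowed, AHI would be most likely to enter when fatigue tracks AHI, which is where the distortion is greatest.

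Second, the numbers rest on an assumed AHI distribution and an unknown dose-response shape. This also stands. Under a pure step the estimate is unbiased and only less precise. Protocol section 7 says that "AHI does not correlate strongly with most relevant OSA co-morbidities", but that is not specific to fatigue and does not settle the shape.

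Third, the information is moved, not lost. A joint two-degree-of-freedom test of OSA and AHI had power of 0.66 to 0.99 across the simulated scenarios, and the group contrast can be rebuilt from the fit. The SAP plans neither, so this softens the point without answering it.

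Fourth, the protocol's Aim 1 also foresees a model to predict fatigue, where using both terms is legitimate. The SAP's regression is instead framed as an adjusted association with OSA status, and for that purpose the OSA coefficient has to be interpretable.

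**Conclusion.** The concern holds. If the listed covariates are used, the Aim 1 regression does not estimate the adjusted OSA versus non-OSA difference. This follows from the definition of OSA and needs no data. The size does depend on assumptions: in the scenarios above, the effect ranges from a loss of precision alone (pure step) to a coefficient near zero. The near-zero result arises only when fatigue is linear in AHI.

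The unadjusted t-test, its stated power and the sample size are unaffected. Aims 2 and 3 are also outside the point. Their comparisons are made among people who all have OSA, as in "We will evaluate if there is a difference in PVT in OSA participants with low vs high AT using a two-sample t-test", and AHI does not define the groups compared. This should be fixed before analysis, but it does not threaten the primary test.

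**What to change.** In the SAP's Aim 1 Statistical Analysis Plan, take AHI off the covariate list for the model that contains OSA status. If severity is of interest, add either a separate, labelled model with AHI in place of OSA status, or an analysis of AHI within the OSA group only. If a prediction model using both terms is wanted, label it as such and do not interpret its OSA coefficient as the adjusted effect. AHI adjustment in Aims 2 and 3 can stay.

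The cost is a change of wording and at most one extra model. No new data are needed, and the primary test and sample size do not change.

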Statistical Analysis Plan: To test change over time after 3 months of PAP therapy in the PLWH+OSA group, we will compare endothelial dysfunction (EndoPAT) at baseline versus 3 months via a paired t-test. Based on Itzhaki and colleagues, we anticipate a mean endothelial function of 1.77 (SD 0.4) in those with untreated OSA, and that a delta of 0.3 represents a clinically important difference based on the effect size of treatment of OSA observed in our prior studies (Ref 127). Assuming a change in mean endothelial function of 0.5 in those with high LG induced OSA vs a change of just 0.2 in those with low LG OSA, we will have adequate power (beta >0.82) to detect this difference between the two groups (alpha = 0.05). As a sensitivity analysis, we will consider multiple regression models adjusting for additional covariates such as age, AHI, medications, mean sleep duration as assessed by actigraphy, and inflammation as assessed by CRP or IL-6 may be included in the modeling if significantly associated with outcome (p<0.10).

References

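### Aim 2A: splitting arousal threshold at the median and using a t-test gives about 63% power, not above 80%; a continuous analysis would probably do better but does not guarantee 80%

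*SAP*

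**What the plan says.** The SAP's sample size paragraph for Aim 2 starts from this expectation: "Of the 120 PLWH studied in Aim 1, we believe that at least 60 will have OSA". It then fixes the grouping: "We will split the cohort of those with OSA into high and low arousal threshold at the median value for the group". The assumed means are 3.9 per second (low threshold) and 4.2 per second (high threshold), with "a SD of 0.5 in both groups". It concludes that "we will have adequate power (beta >0.8) to detect a difference between the two groups (alpha = 0.05"). The word beta there must mean power. The analysis paragraph compares PVT "in OSA participants with low vs high AT using a two-sample t-test".

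A regression appears only as a sensitivity analysis for covariates. AHI is one of several candidates, subject to a p<0.10 screen. Neither document says that arousal threshold will enter any model as a continuous variable.

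Protocol section 9 (Overnight Visit #2) describes how the trait is obtained: mask pressure is lowered gradually until an EEG arousal, and this is repeated until three stable values are in hand. Each participant therefore has a number, not a category.

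**The concern.** There are two linked problems. First, the stated power does not look attainable: a difference of 0.6 SD with 30 per group is too small for 80% by a two-sample t-test. Second, the main test discards most of what the research night measures. Participants just either side of the median are treated as opposites, and differences within each half are ignored. The cut also depends on who enrols, so low and high have no fixed meaning outside this sample.

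In addition, the hypothesis is about people with OSA of like severity, but the t-test neither stratifies nor adjusts for AHI. The risk is a null result for 2A that reflects the analysis and the sample size rather than the physiology.

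**Working it through.** **Inputs (SAP, Aim 2, Sample Size Justification).** 60 with OSA; median split, so 30 versus 30; difference 4.2 − 3.9 = 0.3; SD 0.5 within each group; alpha 0.05. Sidedness is not given for Aim 2A. Two-sided is assumed, as in the Aim 1 calculation, and one-sided is shown as well.

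**Step 1: the SAP's own figure.** Standardised difference d = 0.3/0.5 = 0.6. Noncentrality = d × √(n/2) = 0.6 × √15 = 2.32, with 58 degrees of freedom.

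- Two-sided power: 62.8% (noncentral t); 64.2% (normal approximation).
- One-sided power: 74.3%; 75.1%.
- Needed for 80% two-sided: 45 per group (44 by the normal approximation), so 88 to 90 with OSA; or an SD just under 0.41 with 30 per group.
- Power above 80% appears only under designs that do not apply: 60 per group gives 90%, and 30 pairs with an SD of differences of 0.5 gives 89%.

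**Step 2: the same effect on the continuous scale.** Assume a normal trait and a linear effect; neither is given in the documents. The two median halves then differ by 2√(2/π) = 1.596 trait SDs.

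- Slope = 0.3/1.596 = 0.188 per trait SD.
- Total variance = 0.5² + (0.3/2)² = 0.25 + 0.0225 = 0.2725.
- Correlation = 0.188/√0.2725 = 0.360.
- Fisher z at n = 60: atanh(0.360) × √57 − 1.96 = 0.89, power 81%.
- Simulation of the slope test: 82%. The median split in the same simulated data: 62%, slightly below Step 1 because the trait gap between halves varies from sample to sample.

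**Step 3: add AHI and allow for losses (simulation, two-sided 0.05).** AHI is assumed to have no effect of its own on PVT. Its correlation with arousal threshold is not in the documents, so a range is shown.

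| n with data | Median split | Continuous, no AHI | With AHI, corr. 0 | With AHI, corr. 0.3 | With AHI, corr. 0.5 |
|---|---|---|---|---|---|
| 60 | 62% | 82% | 81% | 78% | 70% |
| 54 (10% lost) | 57% | 78% | 77% | 73% | 65% |
| 48 (20% lost) | 52% | 72% | 71% | 68% | 60% |

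The losses are illustrative. The SAP's 10% allowance (134 enrolled for 120 evaluable) protects Aim 1; nothing separate covers loss before Overnight Visit #2.

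**Step 4: other shapes (n = 60, no AHI, the 0.3 gap between halves kept).**

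| Assumed trait and effect | Continuous | Median split |
|---|---|---|
| Right-skewed (lognormal) trait, linear effect | 87% | 62% |
| Same trait, effect linear in its log, analysed untransformed | 77% | 61% |
| Uniform trait, linear effect | 75% | 61% |
| Effect flattening moderately at both ends | 70% | 61% |
| Effect flattening strongly at both ends | 61% | 60% |
| True step at the median | 43% | 53% |

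**The case against.** The strongest defence is that both documents pose the question as low versus high threshold, and the t-test answers it. The rule is prespecified and simple. That stands as far as validity goes. A reader might infer from a data-dependent cut that the type I error is inflated. The documents do not support this: the cut is fixed in advance at the median and does not look at PVT, so there is no search for a favourable cut-point. The defence does not rescue the power statement, which fails under the SAP's own design.

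The SAP also says at least 60, so more might be found. But 80% needs about 90 of 120, a 75% prevalence against the 50% planned. Even the 70% reported for one cohort in protocol section 7 gives 0.70 × 120 = 84.

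A second line of objection limits the remedy, and it stands. It is tempting to say that the continuous analysis restores the claimed 80% with no extra patients. That holds only without AHI, with all 60 contributing, a roughly normal trait and a linear effect. A figure of about 85% can be reached by reading 0.5 as the overall SD, but the SAP says "a SD of 0.5 in both groups", which is within-group. Adjustment could also raise power if AHI explains variance in PVT; the documents give no basis for assuming so.

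Finally, one might extend the criticism and its figures to loop gain. The Aim 3 text speaks of "a change of just 0.2 in those with low LG OSA" but gives no cut-point, its named test is a paired before-after comparison, and Hypothesis 2B has no stated test. The median rule and these power figures belong to Aim 2A only.

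**Conclusion.** The concern holds for Aim 2A. The claim of power above 0.8 is not supported: the planned test has about 63% (two-sided) on the SAP's own inputs, a 37% chance of missing the effect it assumes. This part needs nothing beyond those inputs, and the one-sided version fails too.

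That a continuous analysis would improve matters is likely rather than certain. Under normality and linearity the gain is about 20 percentage points before AHI, and with AHI it remains at each correlation examined. Its margin over 80% is thin even in the best case. It vanishes with modest losses or a moderate AHI-threshold correlation. The advantage over the split shrinks for a flattening effect and reverses for a true step at the median, a shape neither document proposes.

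**What to change.** In the SAP, Aim 2:

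- Make the primary 2A analysis a linear regression of reciprocal reaction time on continuous arousal threshold, with AHI in the model by prespecification and not subject to the p<0.10 screen. Report the slope with its 95% confidence interval.
- Keep the median split as a descriptive display.
- Prespecify a real check of linearity: a scatterplot with a smoother, a quadratic or spline term, or a transform chosen in advance. Two group means cannot show curvature, so the retained split cannot serve as this check.
- Replace the power statement: about 63% for the split as planned; for the regression, the range in the working table with its assumptions and an allowance for loss before Overnight Visit #2. Write power, not beta.

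Using loop gain as a continuous variable in Hypothesis 2B and the Aim 3 endotype comparison is a suggestion on the same principle, without a power figure attached.

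The cost is SAP wording: no new patients, visits or measurements. The downside is reliance on near-linearity.

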6. SPECIFIC AIMS

Aim 1: To compare the symptoms of PLWH+OSA vs. PLWH–OSA. This aim will allow us to test the hypothesis that fatigue is overexpressed in PLWH+OSA compared to PLWH–OSA, independent of known covariates. We will develop a multivariate model to predict fatigue based on clinical accessible data.

Aim 2: In those PLWH found to have OSA, we will:

a. Compare neurocognitive performance [psychomotor vigilance test (primary outcome), NIH Toolbox Cognition] in PLWH+OSA with low arousal threshold vs. those with a high arousal threshold. We hypothesize that stratified for similar disease severity, low arousal threshold induced OSA yields worse neurocognitive dysfunction compared to equal severity OSA with high arousal threshold.

b. Compare endothelial function (arterial tonometry) in PLWH+OSA with high loop gain (ventilatory instability with associated hypoxemia/hypercapnia) vs. those with low LG, to test the hypothesis that stratified for similar disease severity, LG-induced OSA yields worse endothelial function compared to equal severity OSA with low LG.

Aim 3: To test in PLWH+OSA whether 3 months of PAP treatment results in changes in OSA manifestations. This aim will allow us to test the hypothesis that endotype underlying OSA will be predictive of the specific clinical improvements seen in adherent users of PAP therapy. For example, those with high LG at baseline will have the greatest improvement in endothelial dysfunction with PAP therapy compared to other OSA patients with similar disease severity as measured by AHI.

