10. HUMAN SUBJECTS

People living with HIV (n=120) will be recruited into the study to undergo a standard sleep study (polysomnogram, PSG), a research sleep study, and PAP trial.

Inclusion Criteria:

- Ages 18-65 years old
- BMI 20 – 35 kg/m²
- Physician diagnosis of HIV and viral suppression

Exclusion Criteria:

- Pregnancy

- Inability to complete study procedures, such as questionnaires that are only available/validated in English.
- Already on effective therapy and adherent to treatment for OSA
- Other known untreated sleep fragmenting disorder, such as periodic limb movement disorder, or narcolepsy

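### Aim 2A claims power above 0.8 for the PVT comparison; its own inputs give about 63% two-sided (74% one-sided)

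*SAP*

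**What the plan says.** The SAP's Sample Size Justification under Aim 2 takes its numbers from Aim 1: "Of the 120 PLWH studied in Aim 1, we believe that at least 60 will have OSA". The Aim 1 justification expects 50% prevalence among 120 evaluable participants, "such that 60 subjects will have OSA and 60 will not". The grouping rule for Aim 2A is: "We will split the cohort of those with OSA into high and low arousal threshold at the median value for the group".

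The Aim 2 text names PVT as the main outcome. It assumes mean reciprocal reaction times of 3.9 s⁻¹ (low threshold) and 4.2 s⁻¹ (high threshold), with an SD of 0.5 in each group and alpha 0.05, and concludes that "we will have adequate power (beta >0.8) to detect a difference between the two groups". The planned test is a two-sample t-test. In section 6 of the protocol, PVT appears under Aim 2a as "psychomotor vigilance test (primary outcome").

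The Aim 2A power sentence does not say whether the test is one- or two-sided. The SAP's opening Statistical Considerations make tests of secondary outcomes two-sided, and the Aim 1 power is explicitly two-sided.

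**The concern.** Two things in the sentence look wrong. The first is notation: beta is the type II error rate, so a beta above 0.8 would mean power below 20%. The words around it show that power above 0.8 is meant, so this is a slip.

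The second is the figure. A standardised difference of 0.6 with 30 per group is well short of what 80% power requires. The Aim 3 statement makes this visible: it uses the same absolute difference, 0.3, with a smaller SD (0.4 against 0.5), and claims only slightly more power: "we will have adequate power (beta >0.82) to detect this difference between the two groups (alpha = 0.05").

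At stake is how an Aim 2A result will be read. With a stated power above 80%, a non-significant PVT comparison would be taken as fair evidence against the arousal-threshold hypothesis. If the true power is nearer 63%, a real difference of the size the SAP calls clinically important would be missed more than a third of the time.

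**Working it through.** **Inputs** (SAP, Aim 1 and Aim 2 sample-size paragraphs)

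- With OSA: 120 × 0.5 = 60. The median split gives n = 30 per half. The 30 is derived; it is not printed.
- Difference: 4.2 − 3.9 = 0.3 s⁻¹. SD 0.5 in both halves, so d = 0.3 / 0.5 = 0.6.
- Alpha 0.05, two-sample t-test. Stated power: above 0.8.

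**Power at the planned size**

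Degrees of freedom: 2n − 2 = 58. Noncentrality: d × √(n/2) = 0.6 × √15 = 2.324.

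- Two-sided, critical t = 2.002: noncentral-t power = **0.628**. A simulation of 200,000 trials also gives 0.628.
- One-sided, critical t = 1.672: power = **0.743** (simulation 0.744).
- Normal approximation, two-sided: Φ(2.324 − 1.960) = 0.642.
- Normal approximation, one-sided: Φ(2.324 − 1.645) = 0.751.

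None of these reproduces a figure above 0.8.

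**Could another group size explain the claim?**

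| Scenario | Per half | Two-sided | One-sided |
|---|---|---|---|
| 120 recruited, 10% lost, 50% OSA | 27 | 0.581 | 0.702 |
| Planned 60 with OSA | 30 | 0.628 | 0.743 |
| All 134 enrolled, 50% OSA | 33.5 | 0.677 | 0.784 |
| 120 evaluable, 70% OSA | 42 | 0.776 | 0.860 |
| One short of two-sided 80% | 44 | 0.795 | – |
| Reaches two-sided 80% | 45 | 0.804 | 0.881 |
| 60 in each half | 60 | 0.903 | 0.948 |

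Two-sided 80% needs 90 participants with OSA, or 90 / 120 = 75% prevalence. One-sided 80% needs about 35 to 36 per half, or 70 to 72 with OSA. The first row is an assumed combination. The protocol's Human Subjects section says "People living with HIV (n=120) will be recruited into the study", whereas the SAP says "To account for 10% attrition, we will enroll 134 subjects to achieve 120 evaluable subjects". If only 120 were recruited and the 10% loss occurred, 120 × 0.9 × 0.5 = 54 would have OSA, or 27 per half.

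**Detectable difference and precision**

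- With 30 per half, 80% two-sided power needs d = 0.736, a difference of 0.736 × 0.5 = 0.368 s⁻¹. With 27 per half it is 0.388 s⁻¹.
- For a difference of 0.3 to be detectable with 80% power at 30 per half, the SD would have to be 0.3 / 0.736 ≈ 0.41.
- Expected 95% CI half-width at 30 per half: 2.002 × 0.5 × √(2/30) = 0.258 s⁻¹. An observed difference between 0.300 − 0.258 = 0.042 and 0.258 would therefore be non-significant while the interval still includes 0.30.

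**Check of the method on the neighbouring claims**

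- Aim 3: difference 0.5 − 0.2 = 0.3, SD 0.4, 30 per half, so d = 0.75. The normal approximation gives Φ(0.75 × √15 − 1.960) = 0.828 two-sided, in line with the stated figure above 0.82; the t-based value is 0.815. This takes 0.4 as the SD of change in each half, which the SAP does not say.
- Aim 1: 60 against 60, difference 6, SD 12, so d = 0.5. This gives 0.782 (normal) or 0.775 (t), against a stated figure of approximately 80%.

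The method comes close to both neighbouring figures but not to the one for Aim 2A.

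**The case against.** The best defence is that 60 is a floor. The SAP expects at least that many OSA cases, and the protocol's background cites a cohort of people with HIV in which 70% had OSA. That prevalence would give 84 cases and 42 per half. Even so, two-sided power would be 0.776. Sixty is also the only number planned on: the Aim 1 calculation uses it, and section 26 of the protocol anticipates diagnosing 60 people.

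A one-sided test does not rescue the figure at the planned size (0.743). It is also hard to square with the SAP's rule that secondary outcomes are tested two-sided, which covers PVT if FACIT-F is the study-wide primary outcome. Some doubt about sidedness remains because the protocol calls PVT primary within Aim 2a.

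Two supporting points carry limited weight. The Aim 3 match depends on reading a cross-sectional SD as an SD of change, and one-sided values near 0.89 would also satisfy its claim, so it cannot settle sidedness. The 27-per-half case combines figures from two documents in a way neither states. The conclusion needs neither.

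On importance, the study is sized on FACIT-F in Aim 1. The error changes no planned test or estimate, and the SAP commits to 95% confidence intervals, which will show the imprecision. That limits the harm but leaves a wrong figure for the outcome on which Aim 2A is judged.

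**Conclusion.** The concern holds. Under the SAP's own assumptions, power for the Aim 2A comparison is about 63% two-sided, roughly 17 points below the claim, and about 74% one-sided. The chance of missing a true difference of 0.30 s⁻¹ is therefore about 37% (26% one-sided), where the text implies under 20%.

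This rests on 60 usable participants with OSA, an even median split, a common SD of 0.5 and a t-test at alpha 0.05. More OSA cases than planned would raise the power; any loss before a usable arousal threshold is obtained would lower it. How the stated figure arose cannot be determined from the documents.

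**What to change.** In the Aim 2 sample-size paragraph of the SAP:

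1. Replace *beta* with power. The Aim 3 statement has the same slip.
2. State whether the Aim 2A test is one- or two-sided.
3. Restate the power as about 63% (two-sided) for 30 against 30 with a difference of 0.30 s⁻¹ and SD 0.5, or give 0.37 s⁻¹ as the difference detectable with 80% power.
4. Add that losses between Aim 1 and a usable arousal-threshold measurement reduce this further; for illustration, 27 against 27 gives about 58%.

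These are changes of wording only. Recruitment, procedures and the planned test stay as they are. The cost is a less favourable stated power for Aim 2A, and a non-significant PVT result should then be reported with its confidence interval and not read as evidence of no difference.
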